### 8.3 Changes in Planned Analyses from SAP V2.0 to SAP V3.0

The main changes from SAP V2.0 to SAP V3.0 are described below.

1. In Section 3.5.2, the estimated numbers of OS events at each of OS interim analyses and final analysis are provided.
2. In Section 6.3, Lymph Node Response Rate and Hematological Improvement Rate are removed from the list of key secondary efficacy endpoints and removed from the hierarchy of inferential testing in secondary endpoints.
3. In Section 7.2.1.3, for selected subgroups, additional analyses of PFS are added. These include the estimate and 95% CI for the median by treatment group, and the Kaplan-Meier plot by treatment group.
4. In Section 7.2.2.1, for selected subgroups, summaries of BOR, estimated ORR and its 2-sided 95% CI for each treatment group are added.

## 10 APPENDICES

### 10.1 Appendix A: Primary PFS Event/Censoring Method

Censoring of PFS will be performed as detailed in the table below.

Situation	Date of Event or Censoring	Outcome
No adequate baseline disease status assessment	Date of randomization	Censored
No adequate post-baseline disease status assessment unless death occurs prior to first post-baseline assessment	Date of randomization + 1	Censored
No documented progression or death before data cutoff	Date of last adequate disease status assessment	Censored
Documented progression with $\leq 1$ missing scheduled disease status assessment before progression	Date of the earliest assessment that results in a finding of unequivocal progression	Event
Death before progression being documented with $\leq 1$ missing scheduled disease status assessment before death	Date of death	Event
Documented progression or death following a long gap between adequate disease status assessments (eg, 2 or more consecutive missed scheduled disease status assessments)	Date of last adequate disease status assessment before the gap	Censored
New anticancer treatment or procedure started before documented progression	Date of last adequate disease status assessment prior to new anticancer treatment	Censored

Note: Disease status assessment includes CT scans (chest, abdomen and pelvis), bone marrow aspirate and/or biopsy (may not be required of all subjects at all scheduled disease status assessments), CBC and differential count, focused physical examination, disease related constitutional symptoms for disease assessment, and ECOG performance status. An adequate baseline disease status assessment is any baseline disease status assessment that include WBC counts and CT scans. An adequate post-baseline disease status assessment is any disease status assessment for which a disease status (eg, CR, CRi, PR, PRwL, SD, and PD) is arrived per protocol-defined criteria by the IRC (for IRC assessment) or investigator (for investigator assessment).

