- Hematology laboratory parameters*: red blood cell (RBC) count, hemoglobin, hematocrit, platelets, white blood cell count with 5-part differential (neutrophils, lymphocytes, monocytes, eosinophils, basophils) such that an absolute neutrophil count (ANC) and an ALC can be derived if it is not already provided as part of the laboratory analysis, and coombs testing (direct and indirect). Documentation of hematology labs within 7 days prior to randomization is required to confirm presence or absence of Grade 4 cytopenia for stratification at randomization.
- Coagulation laboratory parameters* including prothrombin time (PT), and activated partial thromboplastin time (aPTT). For subjects receiving anticoagulation therapy affecting the PT, an International normalized ratio (INR) must be obtained.
- Anti-hepatitis C antibody (HCV Ab), hepatitis B surface antigen (HBsAg) and hepatitis B core antibody (HBcAb).
- Laboratory studies to assess the status of prior or current Cytomegalovirus (CMV) and Epstein-Barr virus (EBV) infection. These may include any or all of the following: CMV Ab (via a serology) and antigen [viral load detection via polymerase chain reaction (PCR)] or immunohistochemistry (pp65 CMV) and Epstein-Barr virus serology.
- Serum pregnancy test for WCBP (must be performed within 7 days of randomization)
- HIV test for all subjects without documentation of a prior negative HIV test
- Baseline disease assessments, which include:
 - CT scans of chest, abdomen and pelvis are required for all subjects. Other scans may be performed (eg, head/neck CT) if clinically indicated or if the area is a site of known disease. Copies of all imaging/radiology films will be sent to a central laboratory for independent review.
 - **Note:** Magnetic resonance imaging (MRI) may be substituted if clinically indicated, but the modality chosen to evaluate each individual subject should be the same throughout the duration of the study.
 - Bone marrow aspirate and/or bone marrow biopsy (unless clinically contraindicated).

** ECOG, QoL, hematology, liver function tests, blood chemistry, or coagulation evaluations may be performed within 7 days prior to study treatment (predose Cycle 1 Day 1). If these Screening evaluations are performed within 7 days of Cycle 1 Day 1, these Screening results can be used in place of the Cycle 1 Day 1 assessments.*

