- If a new lesion or isolated increase in target lesion(s) may be attributed to another cause (eg, infection), these findings alone should not be considered to determine progressive disease, especially when observed in the setting of reduced lymph node size or organomegaly, or improvement in hemoglobin/platelets. Radiological persistence of these findings for >4 weeks is likely to indicate disease progression (CT scan confirmation required)

Table 12: SLL Response Criteria (modified from IWG) ^{2, 22}

Response	Lymph Nodes ^a	Spleen/Liver	Blood Lymphocytes	Bone Marrow ^b
Complete Response (CR)	Regression to normal size	Normal size; nodules not present	< 4000/ μ L	If infiltrate present at screening, infiltrate cleared on repeat biopsy
Partial Response (PR) ^c	Decrease \geq 50% in SPD of up to 6 largest masses; no increase in size of other nodes	Decrease \geq 50% in SPD of nodules (or greatest transverse diameter for single lesion); no increase in size of liver or spleen	Decrease \geq 50% from baseline or < 4,000/ μ L	Irrelevant if positive prior to therapy; cell type should be specified
Stable Disease (SD)	Failure to achieve CR/PR criteria or progressive disease			
Progressive Disease (PD) ^{d,e,f}	New lesions (> 1.5 cm) or increase \geq 50% in the SPD from nadir of more than 1 node, or \geq 50% increase in the longest diameter of a node > 1 cm in short axis	> 50% increase from nadir in the SPD of any previous nodules; unequivocal increase in liver/spleen size or de novo appearance of nodules	Increase \geq 50% over baseline or nadir (whichever is lowest) and \geq 5,000/ μ L	

- Evaluated by CT (or MRI) with sum of the products (SPD) of multiple (up to 6) lymph nodes determined. Use of Positron Emission Tomography (PET) imaging is not indicated in CLL/SLL.
- Subjects with CR by CT (or MRI) assessment of lymph nodes, liver/spleen, and peripheral blood without a negative bone marrow result (at baseline or at time of response assessment) will be considered a PR.
- PRwL: subjects who have a \geq 50% reduction in lymphadenopathy, no organomegaly and a negative bone marrow (at baseline or at time of response assessment) with isolated progressive lymphocytosis (blood lymphocytes \geq 4,000/ μ L).
- PD must be confirmed by CT (or MRI) scan

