9.4 EFFICACY ANALYSES

9.4.1 Analysis of Primary Efficacy Endpoint

The primary efficacy endpoint is PFS based on disease status as determined by blinded, independent, central review and will be analyzed using the ITT analysis set.

Censoring of PFS will be performed as detailed in the table below. Additional clarifications will be provided in the SAP as needed.

Table 13: Primary PFS Censoring / Event Methodology

Situation	Date of Event or Censoring	Outcome
No adequate baseline disease status assessment	Date of randomization	Censored
No adequate post-baseline disease status assessment unless death occurs prior to first post-baseline assessment	Date of randomization + 1	Censored
No documented progression or death before data cutoff	Date of last adequate disease status assessment	Censored
Documented progression with ≤ 1 missing scheduled disease status assessment before progression	Date of the earliest assessment that results in a finding of unequivocal progression	Event
Death before progression being documented with ≤ 1 missing scheduled disease status assessment before death	Date of death	Event
Documented progression or death following a long gap between adequate disease status assessments (eg, 2 or more consecutive missed scheduled disease status assessments)	Date of last adequate disease status assessment before the gap	Censored
New anticancer treatment or procedure started before documented progression	Date of last adequate disease status assessment	Censored

Note: Disease status assessment includes CT scans (chest, abdomen and pelvis), bone marrow aspirate and/or biopsy (may not be required of all subjects at all scheduled disease status assessments), CBC and differential count, focused physical examination, disease related constitutional symptoms for disease assessment, and ECOG performance status. An adequate disease status assessment is any disease status assessment for which the blinded independent central review is able to arrive at a disease status (eg, CR, CRi, PR, PRwL, SD, and PD) per protocol-defined criteria.

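### SAP Appendix A ties an adequate baseline to CT although the protocol permits MRI, so read literally an MRI-only baseline is censored at randomization in the primary PFS analysis

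*SAP*

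**What the plan says.** SAP V4.0 Appendix A sets the event and censoring rules for primary PFS. Its first row, "No adequate baseline disease status assessment", gives censoring at the date of randomization and has no exception for death or progression. Its second row does carry one: "No adequate post-baseline disease status assessment unless death occurs prior to first post-baseline assessment". The note under the table defines the baseline term: "An adequate baseline disease status assessment is any baseline disease status assessment that include WBC counts and CT scans". Post-baseline adequacy, in the same note, names no modality; it asks only that the IRC or the investigator reach a disease status. SAP V1.0 has no baseline clause; it appears from V2.0.

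The protocol allows another modality at baseline. Section 6.2.1, under the baseline disease assessments, says "Magnetic resonance imaging (MRI) may be substituted if clinically indicated, but the modality chosen to evaluate each individual subject should be the same throughout" the study. Table 1 note g, Table 5 note e and Section 6.3.9.1 say the same. Protocol Table 13 has the same first censoring row but no separate baseline definition. An adequate assessment there is "any disease status assessment for which the blinded independent central review is able to arrive at a disease status".

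Three other SAP sections rely on these rules. Section 7.2.1.2 analyses investigator-assessed PFS by the primary methods. Appendix B (EFS) repeats the first row without defining its terms. Section 7.2.2.5 applies the Appendix A censoring method to DOR.

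**The concern.** A subject can follow the protocol exactly, with MRI at screening and MRI thereafter, and still fail the SAP's definition of an adequate baseline. The literal result is censoring at time zero, so the subject is in no risk set of the log-rank test or the Cox model. Later scans may be adequate by the SAP's own post-baseline rule and still go unused. A death, which needs no imaging to establish, would go unused too.

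The outputs would also disagree with each other. Under SAP 7.2.2.1 every subject in the analysis set stays in the ORR denominator, so one person could be a responder for ORR and contribute nothing to PFS. For DOR, the same person would be censored on a date before the response began. None of the PFS sensitivity analyses in 7.2.1.2 changes the baseline rule, so none would reveal the loss.

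**Working it through.** **1. Trace one subject through the text.** Take a subject with screening WBC counts and MRI in place of CT, MRI throughout, and progression later documented by the IRC with no missed assessment.

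- Protocol: imaging is compliant (6.2.1, 6.3.9.1).
- SAP baseline definition: WBC counts present, CT absent, so not adequate.
- Appendix A, first row: censored at randomization.
- Appendix A, fourth row (documented progression with at most one missed assessment): event at the date of progression.

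Both rows fit, and the table does not say which prevails. The first row is the more natural choice, because only the second row carries an exception. SAP 5.1 leaves the detailed algorithm to the ADaM specifications, which are not among the documents.

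**2. Reproduce the plan's own figures.** Inputs from SAP 3.2: 185 events, hazard ratio 0.6, one-sided alpha 0.025, 1:1 allocation, medians 9 and 15 months, 300 subjects, 4% dropout per year.

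Power = Φ(|ln 0.6| × √d / 2 − 1.960). With d = 185: 0.5108 × 13.601 / 2 − 1.960 = 1.514, so power = 93.5%. With the interim look, it is 93.4% counting the efficacy bound only and 93.2% if the futility bound is also followed. The plan says approximately 93%.

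Timing uses exponential PFS with hazard λ = ln 2 / median in each arm and dropout hazard η = −ln(0.96)/12 per month. A subject entering at month g has an observed event by month T with probability λ/(λ+η) × [1 − exp(−(λ+η)(T − g))]. The shape of the ramp-up is my assumption: linear to 30 per month over 11 months, then 30 per month to month 16. That gives 0.5 × 11 × 30 + 5 × 30 = 315, scaled to 300. The model puts 93 events at 16.9 months and 185 at 27.4 months; the plan says about 17 and 27.5. The design reproduces, and nothing in the sample size is in dispute.

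**3. Size the literal rule.** The documents give no share of MRI-only baselines, so 1%, 2% and 5% are assumptions. I take the affected subjects to have the same event rate as the rest.

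| Assumed MRI-only share | Subjects of 300 | 185 × (1 − share) | Power at that count | Countable events at month 27.5 | Month of the 185th countable event |
|---|---|---|---|---|---|
| 0% | 0 | 185 | 93.5% | 185.4 | 27.4 |
| 1% | 3 | 183.2 | 93.3% | 183.6 | 27.7 |
| 2% | 6 | 181.3 | 93.0% | 181.7 | 28.1 |
| 5% | 15 | 175.8 | 92.3% | 176.1 | 29.1 |

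The power column applies only if the cutoff is fixed in calendar time. SAP 3.5.1 makes the final analysis event-driven, at approximately 185 PFS events, so the last column is the relevant one: power is kept and the analysis comes later.

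**The case against.** The best defence is that CT scans is the protocol's own label for imaging that includes permitted MRI. Section 6.3.9.1 carries CT in its title, requires CT at baseline, and then allows MRI. The Table 13 note lists CT as the imaging component without mentioning MRI. The CLL criteria in Table 11 speak only of CT; explicit mention of MRI in the response criteria is confined to the SLL notes to Table 12. The SAP may be using the same shorthand. In addition, inclusion criterion 6 asks for measurable disease assessed by CT, so on an equally literal reading an MRI-only baseline should be rare. Protocol 9.4.1 also expects the SAP to add clarifications, so a separate baseline definition is legitimate in itself.

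Most of this stands, and it reduces both the number affected and the certainty of the consequence. It does not make the clause right. The protocol attaches its MRI allowance to the CT item each time; the SAP note does not, and nothing else in the SAP supplies it.

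A reader might infer more than the text supports:

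- *That the ITT principle is breached.* It is not. SAP 4.1 defines the set as all randomized subjects, and a subject censored at day 0 remains in it while contributing no information.
- *That the comparison is biased.* Baseline imaging is completed before randomization, so its modality cannot depend on the assigned arm.
- *That power is materially lost.* The event-driven final analysis prevents this.
- *That censoring over a documented event is certain.* Row precedence is unstated.

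**Conclusion.** The concern holds as a definitional gap. Applied as written, the SAP's baseline clause excludes a modality that the protocol permits, and the first censoring row would then remove that subject's follow-up and any event from primary PFS, investigator-assessed PFS, EFS and DOR.

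The effect is small: each 1% of MRI-only baselines costs about 1.85 of 185 events (185 × 0.01). Up to an assumed 5%, the final analysis moves by at most about 1.7 months (29.1 − 27.4) with power intact, or power drops by 1.2 points (93.5% − 92.3%) if the calendar is fixed. These figures rest on the assumed shares, on the ramp-up shape, and on the literal reading with the first row taking precedence. They apply only to subjects with no baseline CT at all. The reason to act is that a rule for the primary endpoint in an open-label trial should not depend on how a programmer reads one word.

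**What to change.** Change the Appendix A note so that an adequate baseline needs *WBC counts and CT scans (or MRI where substituted per protocol 6.2.1 or 6.3.9.1)*. State that the definition also governs Appendix B and DOR, and carry it into the ADaM specification. In the same edit, state the order in which the rows apply, including how a death or documented progression is counted when the baseline is inadequate.

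Borrowing the Table 13 adequacy rule for baseline is not a good alternative, because the statuses it lists are post-baseline response categories.

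The cost is one clause, one sentence on precedence and a matching line in the ADaM specification. Admitting permitted MRI excludes no one and leaves the design figures unchanged.

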## 10.2 Appendix B: Event-Free Survival (EFS) Event/Censoring Method

Situation	Date of Event or Censoring	Outcome
No adequate baseline disease status assessment	Date of randomization	Censored
No adequate post-baseline disease status assessment unless death or new anticancer treatment/procedure occurs prior to first post-baseline assessment	Date of randomization + 1	Censored
No documented progression, death or new anticancer treatment/procedure started before data cutoff	Date of last adequate disease status assessment	Censored
Documented progression with $\leq 1$ missing scheduled disease status assessment before progression, and no new anticancer treatment/procedure started before documented progression	Date of the earliest assessment that results in a finding of unequivocal progression	Event
Death before progression being documented with $\leq 1$ missing scheduled disease status assessment before death, and no new anticancer treatment/procedure started before death	Date of death	Event
Documented progression, death or new anticancer treatment/procedure following a long gap between adequate disease status assessments (eg, 2 or more consecutive missed scheduled disease status assessments)	Date of last adequate disease status assessment before the gap	Censored
New anticancer treatment/procedure started before documented progression with $\leq 1$ missing scheduled disease status assessment prior to new anticancer treatment/procedure	Start date of new anticancer treatment/procedure	Event

### 10.3 Appendix C: One-Sided Cochran–Mantel–Haenszel (CMH) Test

The Cochran–Mantel–Haenszel (CMH) test compares binary responses of two treatment groups, adjusting for stratification factors. In the CMH test, the data are arranged in a series of associated  $2 \times 2$  contingency tables, the null hypothesis is that the observed response is independent of the treatment used in any  $2 \times 2$  contingency table.

Let  $O_{hij}$  be the observed frequency of treatment  $i$  ( $i=1$  or  $2$ ) with outcome  $j$  ( $j= 1$  or  $2$ ) in stratum  $h$  and  $E_{hij}$  be the expected frequency of treatment  $i$  ( $i=1$  or  $2$ ) with outcome  $j$  ( $j= 1$  or  $2$ ) in stratum  $h$ , where

$$E_{hij} = \frac{(O_{hi1} + O_{hi2}) \cdot (O_{h1j} + O_{h2j})}{O_{h11} + O_{h12} + O_{h21} + O_{h22}}$$

Also, let  $P_{hij}$  be the probability of outcome being  $j$  given treatment being  $i$  ( $i=1$  or  $2$ ,  $j= 1$  or  $2$ ) in stratum  $h$ . To test the following hypothesis,

$$\begin{aligned} H_0 : P_{h11} &= P_{h21} \text{ for all } h \in \{1, \dots, H\} \\ &\text{versus} \\ H_1 : P_{h11} &> P_{h21} \text{ for at least one } h \in \{1, \dots, H\} \end{aligned}$$

The one-sided Cochran-Mantel-Haenszel Test Statistics is constructed as:

$$Z_{CMH} = \frac{\sum_{h=1}^H (O_{h11} - E_{h11})}{\sqrt{V_{11}}} \sim Z$$

Where

$$V_{11} = Var\left(\sum_{h=1}^H (O_{h11} - E_{h11})\right) = \sum_{h=1}^H \frac{E_{h11} \cdot E_{h22}}{O_{h11} + O_{h12} + O_{h21} + O_{h22} - 1}$$

The test statistic  $Z_{CMH}$  will be compared with standard normal distribution to obtain p-value of the CMH test.

## DOCUMENT HISTORY

Version	Date	Author(s)	Brief Summary of Changes
1.0	02 Oct 2014	[name]	Original
2.0	24 Nov 2015	[name]	Clarified the timing of the 2 nd interim analysis of overall survival; added biomarkers to baseline characteristics; other changes. Refer to Section 8.2 for Details.
3.0	06 Apr 2016	[name]	
In Section 3.5.2, the estimated numbers of OS events at each of OS interim analyses and final analysis are provided.
 
Lymph node response rate and hematological improvement rate are removed from the hierarchy of inferential testing in secondary endpoints.

## LIST OF ABBREVIATIONS

Abbreviation	Description
ADaM	Analysis Data Model
AE	Adverse Event
ANCOVA	Analysis of Covariance
AT	All-Treated
ALT	Alanine Aminotransferase
ANC	Absolute Neutrophil Count
AST	Aspartate Aminotransferase
ATC	Anatomical Therapeutic Chemical
BID	Twice a day
BOR	Best Overall Response
BUN	Blood Urea Nitrogen
CI	Confidence Interval
CLL	Chronic Lymphocytic Leukemia
CMH	Cochran–Mantel–Haenszel
CO2	Bicarbonate
CR	Complete Response
CRi	Complete Response with Incomplete Marrow Recovery
CS	Abnormal and Clinically Significant
CTCAE	Common Terminology Criteria for Adverse Events
DOR	Duration of Response
ECG	Electrocardiogram
ECOG	Eastern Cooperative Oncology Group
eCRF	Electronic Case Report Form
eDISH	Evaluation of Drug Induced Serious Hepatotoxicity
EQ-5D	European Quality of Life-5 Dimensions
FACIT-F	Functional Assessment of Chronic Illness Therapy-Fatigue
FACT-G	The Functional Assessment of Cancer Therapy - General

Abbreviation	Description
HR	Hazard Ratio
IDMC	Independent Data Monitoring Committee
IPI-145	(S)-3-(1-(9H-purin-6-ylamino)ethyl)-8-chloro-2-phenylisoquinolin-1(2H)-one
IPCW	Inverse Probability of Censoring Weighted
IRC	Independent Review Committee
IRT	Interactive Response Technology
ITT	Intent-To-Treat
IV	Intravenous
IWCLL	International Workshop on Chronic Lymphocytic Leukemia
IWG	International Working Group
LC/MS/MS	Liquid Chromatography-tandem Mass Spectrometry
LDH	Lactate Dehydrogenase
LFT	Liver Function Test
MedDRA	Medical Dictionary for Regulatory Activities
MEOI	Medical Events of interest
MMRM	Mixed Effect Repeated Measures
MRD	Minimal Residual Disease
NCI	National Cancer Institute
NCS	Abnormal but Not Clinically Significant
NED	No Evidence of Disease
ORR	Overall Response Rate
OS	Overall Survival
PD	Progressive Disease
PFS	Progression-Free Survival
PK	Pharmacokinetics
PP	Per-Protocol
PR	Partial Response
PRwL	PR with Lymphocytosis

---

Abbreviation	Description
PT	Preferred Term
QoL	Quality of Life
RBC	Red Blood Cell
RPSFT	Rank Preserving Structural Failure Time
SAE	Serious Adverse Event
SAP	Statistical Analysis Plan
SD	Stable Disease
SI	Standard International System of Units
SLL	Small Lymphocytic Lymphoma
SOC	System Organ Class
SPD	Sum of Products
TEAE	Treatment Emergent Adverse Event
TTR	Time to Response
UNK	Unknown
VAS	Visual Analog Scale
WHO	World Health Organization
WHO-DD	World Health Organization Drug Dictionary

